6.1.2 Exclusion Criteria

Subjects who meet any of the following criteria will not be eligible to participate:

- 1. Known secondary ITP.
- 2. Body Mass Index (BMI) $>30 \text{ kg/m}^2 \text{ or } >95\%$ for age.
- 3. Any history of arterial or venous thrombosis, including partial or complete thrombosis.
- 4. Subjects with known inherited thrombocytopenia (e.g., MYH-9 disorders).
- 5. History of myelodysplastic syndrome (MDS).
- 6. Known history of congenital heart abnormalities or arrhythmias.
- 7. History of hepatitis B (HBV), hepatitis C (HCV), or human immunodeficiency virus (HIV).
- 8. Known history of disseminated intravascular coagulation (DIC), hemolytic uremic syndrome (HUS), or thrombotic thrombocytopenic purpura (TTP).
- 9. Subjects with Evans syndrome.
- 10. Concurrent malignant disease or previous history of myeloid hematologic malignancies.
- 11. Hemoglobin (Hgb) levels ≤9 g/dL in ages ≥1 year to <6 years and ≤8 g/dL in ages ≥6 to <18 years.
- 12. Estimated glomerular filtration rate (eGFR) <30 mL/min/1.73m².
- 13. Serum total bilirubin $>1.5\times$ the upper limit of normal (ULN) for age, alanine transaminase (ALT) and aspartate aminotransferase (AST) $>3\times$ the ULN for age.
- 14. Known allergy to avatrombopag or any of its excipients.
- 15. Subject is unable to take oral medication, has a malabsorption syndrome, or has known hereditary problems of galactose intolerance, total lactase deficiency or glucose-galactose malabsorption or any other uncontrolled gastrointestinal condition.
- 16. Enrollment in another clinical study with any investigational drug or device within 30 days of Day 1/Visit 2 (or 5 half-lives, whichever is longer); however, participation in observational studies within the previous 30 days is permitted.

- 17. Any clinically relevant abnormality which makes the subject unsuitable for participation in the study, in the opinion of the Investigator.
- 18. Considered unable or unwilling to comply with the study protocol requirements.

6.2 Inclusion and Exclusion Criteria for the Extension Phase

6.2.1 Inclusion Criteria

Subjects who meet all of the following criteria will be eligible to participate in the Extension Phase:

- 1. Subject and/or the LAR must provide consent and/or assent, as applicable, to continue into the open-label Extension Phase. The consent for the Extension Phase will be part of the consent for the Core Phase.
- 2. Completed 12 weeks of treatment in the Core Phase or discontinued the Core Phase early due to lack of treatment effects (see definition of lack of treatment effect in Section 5.3).
- 3. Female subjects of childbearing potential and who are sexually active and male subjects who are sexually active must agree to use highly effective methods of contraception (see Section 8.2).
- 4. Subject and/or the subject's LAR is willing and able to comply with all aspects of the protocol.

6.2.2 Exclusion Criteria

Subjects who meet any of the following criteria will not be eligible to participate in the Extension Phase:

- 1. Significant safety or tolerability concerns with the subject's participation, in the opinion of the Investigator.
- 2. Subjects requiring the following drugs or procedures at the time of enrollment into the Extension Phase:
 - Rituximab
 - Other TPO-RAs
 - Splenectomy
 - Moderate or strong dual inducers or moderate or strong dual inhibitors of CYP2C9 and CYP3A4 (Appendix D).

6.3 Subject and Study Discontinuation

6.3.1 Screen Failures

Subjects and/or their LAR, as applicable, who sign and date the ICF and/or assent form, but who fail to meet all the inclusion criteria or meet any exclusion criteria for the Core Phase, are defined as a screen failure.

The following data will be recorded in the eCRF for screen failed subjects:

• ICF and/or assent form signature date

- Demographic information
- AEs that occur after signing the ICF and/or assent
- Reason for screen failure (e.g., inclusion/exclusion criteria that was not met, etc.)

Subjects may be re-screened with prior approval from the Sponsor.

6.3.2 Early Termination

A subject may be early terminated from the Core Phase or the Extension Phase for any of the following reasons:

- A platelet count $>250\times10^9$ /L after 2 weeks of once weekly dosing for any age cohort.
- Subject or the subject's LAR, as applicable, wishes to withdraw consent/assent for any reason.
- Subject non-compliance or unwillingness to comply with the procedures required by the protocol.
- Occurrence of any medical condition that exposes the subject to substantial risk and/or does not allow the subject to adhere to the requirements of the protocol.
- Any SAE, clinically significant AE, severe laboratory abnormality, intercurrent illness, or other medical condition which indicates to the Investigator that continued participation in the study is not in the best interest of the subject.
- Pregnancy.
- Requirement of a prohibited concomitant medication (Section 8).
- Investigator discretion.
- Sponsor request.
- Termination of the study by the Sponsor or a regulatory agency.

In addition, a subject may be early terminated from the Extension Phase if they have a platelet count $<30\times10^9/L$ after 3 weeks of once daily dosing at the cohort defined maximum dose.

Every effort should be made during the conduct of the study to limit the extent of missing data. Except for subjects who are being withdrawn from the Core Phase due to a lack of treatment effect (Section 5.3), subjects who prematurely discontinue the study drug should remain in the study for collection of data, unless the subject withdraws consent. If a subject is early terminated from the Core Phase of the study after the first dose of study drug, but prior to the end of the PK blood collection (Visit 12/Week 10), consideration should be given to collecting all remaining PK blood draws, if possible.

If a subject is early terminated from the study after randomization, the Early Termination procedures (Section 9.3) should be performed. Subjects withdrawn from the study after randomization will not be replaced, regardless of the reason for withdrawal.

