Lack of treatment effect will be defined as:

- Platelet count remains <30×10⁹/L after more than 3 weeks at the maximum dose of study drug per cohort. Subjects may also be terminated from the Core Phase and directly enrolled into the Extension Phase after 7 days of therapy at the maximum dose if they have dangerously low platelet counts (in the opinion of the Investigator), or
- Subjects who require rescue therapy more than 3 times or continuous rescue therapy for more than 3 weeks.

The Core Phase of the study will last 12 weeks (approximately 84 days), which does not include the 4 week Follow-up Period, with study visits occurring once weekly through the end of Week 12.

Subjects who complete the 12 week Core Phase of the study, or who meet the stopping criteria and are discontinued from the Core Phase, will be eligible to enter the open-label Extension Phase, if they continue to meet the inclusion criteria and do not meet any exclusion criteria for this phase of the study. Subjects and/or the subject's LAR must complete informed consent/assent in order to participate in the Extension Phase of the study. The Extension Phase of the study will last 2 years during which time the subject will have monthly clinic visits. Subjects may be early terminated from the Extension Phase if they have a platelet count $>250\times10^9/L$ after 2 weeks of once weekly dosing for any age cohort or $<30\times10^9/L$ after 3 weeks of once daily dosing at the cohort defined maximum dose.

DOSAGE FORMS AND ROUTE OF ADMINISTRATION: In the Core Phase of the study, subjects will receive avatrombopag or placebo as either the film-coated oral tablet (20 mg per tablet) or as a capsule containing a powder for oral suspension (10 mg per capsule) which can be opened to sprinkle the contents into an appropriate vehicle. Subjects in Cohort 1 (aged \geq 12 to <18 years) and Cohort 2 (aged \geq 6 to <12 years) will receive the oral tablet and subjects in Cohort 3 (aged \geq 1 to <6 years) will receive the powder for suspension in a capsule.

In the Extension Phase of the study, subjects will receive open-label avatrombopag as either the film-coated oral tablet (20 mg per tablet) or as the capsule containing a powder for oral suspension (10 mg per capsule).

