Table 2 Study Drug Starting Dose by Age Cohorta in the Core Phase and Extension Phase

Age Range (Years)	Study Drug Starting Dose (mg)	Formulation
	Cohort 1	
≥12 to <18 20 mg Once Daily Oral Tablet		
Cohort 2		
≥6 to <12	20 mg Once Daily	Oral Tablet
Cohort 3		
≥1 to <6	10 mg Once Daily	Capsule

a: Subject age at the time of randomization will be used. The starting dose of study drug may be revised after scheduled PK/PD and safety reviews (Section 5.1).

Table 3 Study Drug Dose Adjustments in the Core Phase and Extension Phase

Platelet Count (×10 ⁹ /L)	Dose Adjustment or Action
$<50\times10^9/L$ after at least 2 weeks of dosing.	 Increase 1 Dose Level per Table 4. Wait 2 weeks to assess the effects of this regimen and any subsequent dose adjustments.
>150×10 ⁹ /L to ≤250×10 ⁹ /L	 Decrease 1 Dose Level per Table 4. Wait 2 weeks to assess the effects of this regimen and any subsequent dose adjustments.
>250 ×10 ⁹ /L	 Stop study drug. Increase platelet monitoring to twice weekly. When platelet count is ≤100×10⁹/L, decrease 1 Dose Level per Table 4.
<30×10 ⁹ /L after 3 weeks of once daily dosing at the cohort defined maximum dose per Table 4.	Discontinue study drug.
Also see protocol stopping criteria in Section 5.3 and early termination criteria in Section 6.1.6.	
>250×10 ⁹ /L after 2 weeks of once weekly dosing for any age cohort	Discontinue study drug.

 Table 4
 Study Drug Dose Level Titration (Core and Extension)

Dose	Dose Level
Cohort 1 (≥12 to <18 Years) and Cohort 2 (≥6 to <12 Years) Dosed with Oral Tablet	
40 mg Once Daily	6
40 mg Three Times a Week AND 20 mg on the Four Remaining Days of Each Week	5
20 mg Once Daily ^a	4
20 mg Three Times a Week	3
20 mg Twice a Week	2
20 mg Once Weekly	1
Cohort 3 (≥1 to <6 Years) Dosed with Powder for Oral Suspension	
20 mg Once Daily	6
20 mg Three Times a Week AND 10 mg on the Four Remaining Days of Each Week	5
10 mg Once Daily ^a	4
10 mg Three Times a Week	3
10 mg Twice a Week	2
10 mg Once Weekly	1

a: Subject age at the time of randomization will be used. Initial dose regimen based on modeling and simulation. Actual initial dose in Cohort 2 and Cohort 3 may be modified after modeling is completed using data from the previous cohort.

To ensure accuracy of the predictions, PK, platelet response, and safety data will be reviewed by the Sponsor, or the Sponsor's unblinded designee, as described in Section 5.1 and if necessary, adjustments of the dose level may be made following these data reviews.

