7.4 Efficacy Analysis

Unless otherwise stated, all primary and secondary efficacy endpoints defined in Section 3.2.1 will be analyzed for the FAS and PPS.

For the efficacy evaluation of the platelet count responses, platelet counts assessed by local labs will be used. Platelet counts collected via the central lab will be used in the safety assessments of

clinical laboratory tests.

The methods used for efficacy analysis for the Core Phase are summarized in Error! Reference source not found.3. All Cochran-Mantel-Haenzel (CMH) tests at alpha=0.05 within each age cohort will be performed adjusting for baseline platelet count category ($\leq 15 \times 10^9 / L \text{ vs} > 15 \times 10^9 / L$). For the CMH test in the overall group, the test will be performed adjusting for age cohort and baseline platelet count category. Fisher's exact test will be used if the number of durable platelet responders is spare in the strata (less than 3 in a specific subgroup). Durable platelet response with 2-sided 95% exact binomial (Clopper-Pearson) confidence interval (CI) will be provided. The difference in response rate (avatrombopag – placebo) with 2-sided 95% CI (Wald) will also be provided.

Subjects without sufficient data for the determination of response status (i.e., responder versus non-responder) will be treated as non-responders in the analysis.

For the primary efficacy endpoint determination, a subject must have remained in the Core phase through at least Week 10 (to have at least 6 weeks of platelet count data starting from week 5 to either week 12 if the subject completes the core phase or the last week if the subject prematurely terminates the core phase). If a subject terminates the Core phase prior to Week 10, they would be considered a non-responder for the primary efficacy endpoint.

Endpoint	Analysis Method
Primary Efficacy Endpoint	
Durable platelet response defined as proportion of subjects achieving at least 6 out of 8 weekly platelet counts $\geq 50 \times 10^9 / L$ during the last 8 weeks of the 12 week treatment period in the Core Phase in the absence of rescue medication. In the case of rescue medication being used, platelet count assessments from the start date of rescue medication up until 4 weeks after the end date of rescue medication will be excluded from analysis.	CMH test

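### The rule for a platelet count above 250 on once-weekly dosing is worded differently across sections, the SAP leaves its effect on primary scoring open, and Table 3 separately calls for a dose level that Table 4 lacks

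*Protocol*

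**What the plan says.** **The rule for a high count on once-weekly dosing.** Table 3 of the protocol, whose title covers the Core and the Extension, has a row for a count above 250×10⁹/L "after 2 weeks of once weekly dosing for any age cohort". Its action is "Discontinue study drug", and it does not mention leaving a phase. Section 6.3.2 lists the same finding first under "A subject may be early terminated from the Core Phase or the Extension Phase for any of the following reasons". The synopsis (Study Design and Duration) and Section 1.4.1 introduce it with "Subjects may be early terminated from the Extension Phase if they have a platelet count", and SAP 2.1 does the same in near-identical words; none of the three mentions the Core. The Core stopping criteria in Section 5.3 do not list it.

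**Staying in the study.** Section 6.3.2 exempts withdrawal for lack of effect and then says "subjects who prematurely discontinue the study drug should remain in the study for collection of data, unless the subject withdraws consent". Section 11.2.2 repeats the stay-in-study rule.

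**Scoring.** SAP 7.4 says "If a subject terminates the Core phase prior to Week 10, they would be considered a non-responder for the primary efficacy endpoint". SAP 4.1 defines the Core Phase as ending at Visit 14 or on the day study drug is discontinued.

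**Dose levels.** For counts above 150 and up to 250, Table 3 says "Decrease 1 Dose Level per Table 4". After a hold for a count above 250 it says "When platelet count is ≤100×10⁹/L, decrease 1 Dose Level per Table 4". Neither row makes an exception for Level 1, which is once-weekly dosing and the lowest row of Table 4 in every cohort.

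**The concern.** There are two separate problems.

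First, an investigator with a Core child who meets the high-count rule cannot tell from the protocol whether the rule ends drug or ends participation. Table 3 supports the first, the opening list of 6.3.2 permits the second, and the later stay-in-study text of 6.3.2 pulls back toward the first, because over-response is neither lack of effect nor withdrawn consent. The choice matters for the primary endpoint. A child terminated before Week 10 is a non-responder by rule, even if every count in the window so far is at least 50. A child who stops drug and stays may still be evaluable, but only if the SAP accepts counts taken off drug, and it does not say. SAP 4.1 read literally points the other way from the protocol's data-collection rule.

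Second, a child already on once-weekly dosing whose count falls in the decrease range has an instruction that cannot be carried out, because there is no lower level to go to.

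**Working it through.** **1. The plan's own power figure.** Inputs from protocol 11.3: 54 avatrombopag and 18 placebo, durable response 41.3% and 3.4%, Fisher's exact test, α = 0.05 (taken as two-sided, as in 11.2.2). Power is the sum of Bin(x; 54, 0.413) × Bin(y; 18, 0.034) over all outcomes (x, y) with Fisher p ≤ 0.05. The result is 94.5%, so the stated figure of at least 90% is reproduced.

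**2. When the rule can first apply in the Core.** Inputs: start at Level 4 (Table 4), first scheduled titration assessment at Visit 4, Day 15 (Table 7), and a 2-week wait after each adjustment (Table 3). Reaching Level 1 takes 4 − 1 = 3 decreases.
- Day 15 (Week 2): Level 4 to 3
- Day 29 (Week 4): Level 3 to 2
- Day 43 (Week 6): Level 2 to 1
- Day 57 (Week 8): two weeks of once-weekly dosing complete, so the rule can apply

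The other route is repeated holds for counts above 250. With a hold of w weeks and r weeks on drug to the next high count, the rule applies at Week 2 + 3w + 2r + 2. Assuming w = 0.5 to 2 and r = 1 to 2, this runs from 2 + 1.5 + 2 + 2 = Week 7.5 to 2 + 6 + 4 + 2 = Week 14, which is after the Core. The documents do not give w or r.

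**3. What that means for 6 of 8.** The window is Weeks 5 to 12. At Week 8 four counts exist (Weeks 5, 6, 7 and 8). A child with 4 of 4 at or above 50 needs 6 − 4 = 2 more from Weeks 9 to 12.
- *Terminated at Week 8:* non-responder under the Week 10 rule.
- *Drug stopped, child stays, off-drug counts used:* still evaluable, with 2 of the 4 remaining counts needed.
- *Drug stopped, child stays, SAP 4.1 read literally:* the Core ended that day, before Week 10, so the child could again be a non-responder.

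SAP 7.2.2 tabulates leaving the phase and stopping drug as separate events, which argues against the third reading but does not settle it. For the percentage-of-weeks endpoints, SAP 7.4 bases the denominator on weeks on treatment. It has no corresponding statement for the primary endpoint. From Week 10 on, leaving no longer triggers automatic non-response. The scoring question is therefore confined to about Weeks 8-9.

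**4. Size.** One child rescored moves the avatrombopag rate by 1/54 = 1.9 percentage points. If k avatrombopag responders are rescored as non-responders, the assumed rate becomes 0.413 − k/54, and the power from step 1 becomes:
- k = 1 (39.4%): 92.0%
- k = 2 (37.6%): 88.8%
- k = 3 (35.7%): 84.8%
- k = 4 (33.9%): 79.8%
- k = 5 (32.0%): 74.0%

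Here k is an assumption; the documents give no frequency.

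**5. Level 1.** Two Table 3 rows call for one level lower: counts above 150 up to 250, and resumption after a hold for a count above 250. At Level 1 that would be Level 0, which Table 4 does not contain. For a count above 250 once 2 weeks of once-weekly dosing are complete, Table 3 has its own row. The gap therefore arises at Level 1 for counts above 150 up to 250, and for counts above 250 before those 2 weeks are complete.

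**The case against.** The strongest reply is that the texts can be read together: a mandatory drug stop in Table 3, an optional termination in 6.3.2 (which says only that a subject may be terminated), and data collection as the default. That is a reasonable reading, but the protocol does not state it, and it still leaves SAP 4.1 at odds with the default.

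Four stronger readings are tempting, and the documents do not support them.
- A reader might infer that the synopsis, 1.4.1 and SAP 2.1 limit the rule to the Extension. They omit the Core but do not exclude it, and 6.3.2 names both phases.
- A reader might infer that platelet follow-up ends at the high count. It does not. The early termination visit in 9.3 includes a count. Section 4.1.1.3 follows children who do not enter the Extension for 30 days (±7) after the last dose, and the last column of Table 7 includes a platelet count. An over-responder terminated from the Core belongs to that group, since Extension entry (6.2.1) requires completion of the Core or lack of effect. What would be lost is the remaining weekly counts.
- A reader might infer that sites will score the same child differently. This is possible but not shown, because under the literal SAP 4.1 both routes before Week 10 could end as non-response.
- A reader might link the missing level to the scoring problem. They are separate, because the high-count rule has its own row.

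The objection that the exposure is small also stands. The Week 8 path needs three consecutive reductions and then a count above 250, after the weekly amount in Cohorts 1 and 2 has gone from 7 × 20 = 140 mg to 20 mg.

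**Conclusion.** The point holds as a set of inconsistencies that should be reconciled. The high-count rule differs in force (stop drug, or permitted termination) and in stated scope (both phases, or the Extension with the Core unmentioned). The protocol's stay-in-study rule does not fit SAP 4.1, and the SAP does not say whether counts after drug discontinuation enter the primary endpoint. Depending on the reading, a child with 4 of 4 qualifying counts at Week 8 is either an automatic non-responder or still evaluable.

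The effect is limited. It concerns exits at about Weeks 8-9, assuming a first decrease at Visit 4 and 2-week steps. Each child is worth 1.9 points, and the number of such children is unknown. Any bias would mainly count against avatrombopag, so it costs power rather than threatening a false positive. On the sample-size assumptions, two rescored responders would take power just below the stated 90%. The endpoint of two consecutive counts is probably little affected, since such children are likely to have met it already.

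The Level 1 gap is independent of scoring: as written, the instruction cannot be followed for a child already on once-weekly dosing. No view is taken here on which clinical rule is right.

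**What to change.** 1. Reconcile Table 3, Section 6.3.2, the synopsis, Section 1.4.1 and SAP 2.1 to one statement of the phases in which the high-count rule applies and whether it ends drug or participation. The choice is the sponsor's.
2. Reconcile SAP 4.1 and 7.4 with the stay-in-study rule in protocol 6.3.2 and 11.2.2. State whether platelet counts after drug discontinuation are used for the primary endpoint. Where a Core child stops drug but is not withdrawn, collect the scheduled weekly counts through Week 12.
3. Reconcile Tables 3 and 4 for a child already at Level 1. The clinical action is the sponsor's to decide.
4. In the SAP 7.2.2 disposition table, which already reports reasons for stopping drug and for leaving the phase, identify discontinuation for a high platelet count as its own reason.

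The cost is wording in the protocol and SAP and one disposition category. No visits are added, because the weekly counts through Week 12 are already in Table 7. The SAP wording should be settled before database lock and unblinding.

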7 STUDY TREATMENTS

7.1 Treatment Groups

The 12 week Core Phase of this Phase 3b study is randomized, double-blind, and placebo-controlled. At Day 1/Visit 2, subjects will be randomized in a 3:1 ratio to receive either avatrombopag or matching placebo.

The Extension Phase of this study is open-label therefore all subjects will receive avatrombopag.

7.2 Randomization and Blinding

During Day 1/Visit 2 of the Core Phase, after study eligibility has been confirmed, randomization assignment will be performed using interactive response technology (IRT). Randomization will be stratified by age cohort. Subjects will also be stratified by a Baseline platelet count of $\leq 15 \times 10^9/L$ or $>15 \times 10^9/L$ to $<30 \times 10^9/L$ in order to ensure treatment groups are approximately balanced. Following randomization, study drug will be dispensed in a double-blind manner. The Sponsor, the subject, and the clinical site personnel will be blinded to the treatment assignment.

No randomization or blinding is necessary for the Extension Phase as all subjects will receive openlabel avatrombopag.

